**Table XIII. Patency rates at 12 months after iliofemoral venous stenting**

Clinical Category (Limbs)	12-Month Patency Rates		
	Primary	Primary-Assisted	Secondary
Acute (N = 662)	84.0%	91.1%	96.7%
Post-thrombotic (N = 1,175)	80.5%	88.1%	91.9%
Non-thrombotic (N = 901)	94.8%	100.0%	100.0%
Mixed, Acute & Chronic (N = 649)	83.6%	85.0%	93.6%
Mixed; PT and NT (N = 958)	83.8%	92.9%	89.5% 
All Stent Publications (N = 4,247)	85.7%	93.8%	95.2%

 Secondary patency for this cohort is lower than primary-assisted patency since different series are included in the two measures.

### **Quality of Life Measures after Intervention**

Post-intervention Quality of Life measures were not consistently reported in the studies. The post-intervention CEAP, Villalta, VCSS and CIVIQ-20 scores were reported in only four, six, nine and one of the series, respectively. The VEINES score was not reported in any of the series.

The QoL results indicated improvement from pre- to post-intervention, evident in all four indices studied; as listed in **Table XIV**.

**Table XIV. Pre- and post-intervention venous Quality of Life indices.**

Scale	Pre-Intervention	Post-intervention	Change
CEAP	3.8	2.2	1.6
Villalta	17.3	6.6	10.7
VCSS	9.7	3.7	6.0
CIVIQ-20 	64	83	19

### **Results in Medically-Managed Patients**

There were nine series reporting outcome in patients with iliofemoral venous obstruction after medical management alone. A total of 364 subjects and 367 limbs were studied; 58.6% were female with an average age of 48.8 years and mean CEAP 4.2 at presentation. The majority (64.9%) of patients in the medically-managed series were patients with acute iliofemoral venous thrombosis, and the process was on the left in 67.6%, right in 22.9% and bilateral in 9.5%. The follow-up averaged 23 months and, where specified in the publications, the primary treatment modality was heparin follow-up by long-term warfarin anticoagulation. The weighted primary patency rate was 47.1% at 1 year.

### **Data from Publications on CE-Marked Stents for the Iliofemoral Venous Indication**

While there are no stents approved for the iliofemoral venous indication in the US, several are CE marked in Europe (**Table XV**). These include the Cook Zilver Vena, OptiMed sinus-Venous, Veniti Vici, and the Boston Scientific Wallstent. The Wallstent, while the most commonly employed stent for two decades, did not receive CE mark for the iliofemoral venous indication until 2015.

It is not possible to parse data on the on-label venous stents from other, off-label venous stents for most of the publications evaluated in the scientific literature review. Authors rarely report results by type of stent. As well, to date (October 2016) there have been no publications on the Veniti Vici stent and Bard Venovo stent. Noting these limitations, the outcome after on-label venous stenting is reported from a small subset of the articles reviewed and is limited to those reports that specify outcome separately for one of the four CE-marked venous stents.

CIVIQ-20 scores were reported in only one publication. Higher scores mean better quality of life.

The findings in the on-label venous stents are dominated by publications that used the Wallstent (**Table XVI**). While this analysis is limited by the relatively small sample size in the on-label group, currently available data do not reveal marked differences between data from studies on CE marked stents compared to those that used other stents.

**Table XV. Venous stents with CE Mark**

Company	Stent Brand Name	Material	Character	CE Mark
Cook Medical	Zilver Vena	Nitinol	Self-expanding	2011
OptiMed	sinus-Venous	Nitinol	Self-expanding	2012
Veniti	Vici	Nitinol	Self-expanding	2013
Boston Scientific	Wallstent	Elgiloy	Self-expanding	2015 

**Table XVI. Outcome reported from on-label venous stents**

Stent (Series/Limbs)	Primary Patency	Safety			Clinical Villalta Change
		30-day Thrombosis	Stent Fracture	Stent Migration	
Cook Zilver Vena (1/20) 	85.0%	15.0%	NS	NS	NS
OptiMed Sinus (1/80) 	96.3%	NS	NS	NS	6.5
Boston Sci Wallstent (22/2,008)	88.8%	1.7%	1.6%	2.4%	7.6
All CE-Marked Stents (24/2,108)	89.0%	1.8%	1.6%	2.4%	6.6

NS- Not Specified

 While an article in Endovascular Today stated that the Wallstent was recently CE marked, there is no confirmation of same on the Boston Scientific corporate website.

 There were no publications on the Veniti Vici stent.

## **Conclusions**

The results of this Scientific Literature Search suggest that venous stenting was associated with acceptable outcomes in patients presenting with acute, chronic post-thrombotic, and chronic non-thrombotic iliofemoral venous obstruction.

The average age at presentation was 52.7 years, although patients presented throughout all age ranges. Females presented more often than males; 63.5% versus 36.5%, respectively. Treated lesions were more often on the left than the right; 70.0% vs. 20.4%. Bilateral lesions were treated in 9.6% of patients. At baseline, 65.2% of patients were within CEAP 3 or 4 categories; more mild symptomatology was found in 8.7% of cases; 26.4% presented with a healed (C5, 7.5%) or active ulcerations (C6, 18.9%).

The venous stenting procedure was quite safe. Major hemorrhage occurred in 1.1% of patients with access site hematomas in 3.6%. Other access site complications such as false aneurysms or arteriovenous fistulae were very rare as was pulmonary embolism or death within 30 days of the procedure; each occurring in 0.2% or fewer patients. When MAE were defined as the composite occurrence of major procedural bleeding (BARC Type 3a or greater), all-cause mortality, stent thrombosis, pulmonary embolism or stent migration, 5.6% experienced an MAE within 30 days. Stent fracture was reported in 1.4% of patients, with stent dislodgement (at the index procedure) in 0.6% and stent migration (after the index procedure) in 1.6%.

Effectiveness as measured by patency rate was satisfactory. At 1 year, primary, primary-assisted and secondary patency rates were 85.7%, 93.8% and 95.2%, respectively. TLR at 12 months was 8.3%. There did not appear to be substantial differences in outcome between patients treated with off-label or CE-marked venous stents, but the relatively small sample for CE-marked stents precluded a robust analysis.

In summary, iliofemoral venous stenting as reported in the literature appears to be associated with relatively few perioperative and longer-term complications, with a 30-day MAE rate of 5.6% and a primary patency rate of 85.7% at one year.

## Appendix B Definitions

Acute deep vein thrombosis	
Formation of a blood clot (thrombus) in one or more of the deep veins less than 14 days old.
 
Note: this does not include deep venous thrombus contiguous to and occurring as a result of stent occlusion.

Acute success	
 
Device Success: Successful delivery and deployment of the Abre stent in the target lesion with successful removal of the delivery system.
 
Lesion Success: Venographic evidence of <50% final residual stenosis of the stented segment of the target lesion after post-dilation, when applicable, and as assessed by core laboratory.
 
Procedure Success: Lesion success without procedure-related MAEs prior to hospital discharge within 30 days.
 
 
Note: If core laboratory is unable to assess the venographic evidence, site reported data will be used.

Chronic venous obstruction	Obstruction of the deep veins related to a previous deep vein thrombosis or stenosis from external compression > 6 months before study inclusion.
Clinically driven	Defined as the recurrence of symptoms present at baseline or the onset of new symptoms including, but not limited to venous pain, swelling, dermatitis, or ulceration related to the target limb.
Major adverse events (primary endpoint)	
 
All-cause death occurring post-procedure
 
Clinically significant (i.e. symptomatic, confirmed by CT pulmonary angiography) pulmonary embolism
 
Major bleeding complication (procedural)
 
Stent thrombosis confirmed by imaging as assessed by core laboratory
 
Stent migration confirmed by imaging as assessed by core laboratory
 
 
Note: Migration excludes stent dislodgement at the index procedure as may occur with under-sizing of a stent.

Major adverse events (secondary endpoint)	
 
All-cause death occurring post-procedure
 
Clinically significant (i.e. symptomatic, confirmed by CT pulmonary angiography) pulmonary embolism
 
Major bleeding complication (post-procedural)
 
Stent thrombosis confirmed by imaging as assessed by core laboratory
 
Stent migration confirmed by imaging as assessed by core laboratory
 
 
Note: Migration excludes stent dislodgement at the index procedure as may occur with under-sizing of a stent

Major amputation	
Surgical removal of tissue in the target limb above the level of the ankle, requiring a prosthetic limb to ambulate:
 
 
• Above knee amputation (amputation of limb with resection point above the knee)
 
• Below knee amputation (amputation of limb with resection point below the knee and above the ankle)
 

Major bleeding complication	A blood loss leading to transfusion of whole blood or red cells provided hemoglobin drop of 3 g/dL (1.86 mmol/L) or more is related to bleeding occurring during the index procedure through 36 months post-index procedure.
Major bleeding complication (procedural)	A blood loss leading to transfusion of whole blood or red cells provided hemoglobin drop of 3 g/dL (1.86 mmol/L) or more is related to bleeding occurring during the index procedure through 30 days post-index procedure.
Major bleeding complication (post-procedural)	A blood loss leading to transfusion of whole blood or red cells provided hemoglobin drop of 3 g/dL (1.86 mmol/L) or more is related to bleeding occurring at 30 days through 36 months post-index procedure.
Minor amputation	
Surgical removal of tissue in the target limb:
 
 
• Trans-metatarsal amputation (amputation with resection point at the level of the metatarsal bones of the foot)
 
• Toe amputation (amputation of one or more toes)
 

Obstructive lesion	Obstructive lesion is defined as: 
 
i. Occluded, or
 
ii. ≥50% in diameter reduction on venography or IVUS, or
 
iii. ≥50% area reduction on IVUS
 

Point of enrollment	The point of enrollment is the time at which the subject signs and dates the informed consent form.
Point of inclusion	The point of inclusion is the time at which the subject who signed and dated the informed consent form, adhered to all I/E criteria and where the Abre system enters the vasculature.
Postthrombotic syndrome (PTS)	Complication of deep vein thrombosis (DVT) or stenosis of a deep vein with symptoms ≥ 6 months before study inclusion. Symptoms may include brownish discoloration of the skin, itching, swelling, slow-healing sores, pain in the area, fragile skin on the area, which may bruise easily, dry or peeling skin.
Primary assisted patency	Uninterrupted patency of the stented segment of the target lesion with a secondary intervention, also known as an adjunctive treatment (e.g. balloon venoplasty, subsequent stenting, etc.).

Secondary patency	
Patency of the stented segment of the target lesion after subsequent intervention for an occlusion.
 
Note: Confirmed by DUS, evaluated by independent core laboratory. In cases where both DUS and venography were used at the same time point, venography would be used to for the primary assessment.

Serious adverse health consequences (CFR 21-814)	Any significant adverse experience, including those which may be either life-threatening or involve permanent or long term injuries, but excluding injuries that are non-life-threatening and that are temporary and reasonably reversible.
Target lesion	The target lesion is defined as non-malignant venous obstruction within the common iliac, external iliac and/or common femoral vein: the proximal point of the obstruction may extend to the iliac venous confluence of the inferior vena cava and the distal point may be at or above the deep femoral vein.
Target lesion revascularization (TLR)	Any re-intervention of the stented segment of the target lesion.
Target vessel	The target vessel is defined as the common iliac, external iliac and/or common femoral vein.

Stent fracture	
Fracture or breakage of any portion of the stent.
 
Stent Fracture Classification: Determined by X-ray (assessed by core laboratory):
 
 
• Type 0 – No strut fractures
 
• Type I – Single tine fracture
 
• Type II – Multiple tine fractures
 
• Type III – Stent fracture(s) with preserved alignment of the components
 
• Type IV – Stent fracture(s) with mal-alignment of the components
 
• Type V – Stent fracture(s) in a trans-axial spiral configuration
 
 
Stent migration	
Stent migration (as part of primary safety and secondary MAE endpoints): position change of a properly sized venous stent observed with an imaging modality, with displacement of the stent outside of the intended treatment segment after the conclusion of the index procedure, as determined with regard to a reference anatomic structure.
 
Delayed stent migration (as part of secondary endpoint): position change of a venous stent observed with an imaging modality > 1 cm from its original location at the conclusion of the index procedure, as determined with regard to a reference anatomic structure.
 
Stent migration occurs following the proper deployment of a venous stent after the index procedure (i.e. stent movement or dislodgement during the index procedure will not be noted as stent migration).

Stent thrombosis	
Occlusion of the stented venous segment occurring at any time following stent placement.
 
Stent thrombosis may be diagnosed by Duplex Ultrasound. It needs to be confirmed by venogram or IVUS.

Thrombosis	
A total occlusion due to thrombus formation as confirmed by sudden onset of symptoms and documented by DUS and venogram and/or IVUS at the target vessel.

Vein compression syndrome	
A condition in which compression of the common iliac venous outflow tract of the left lower extremity may cause discomfort, swelling, pain, or blood clots

	(deep vein thrombosis) in the iliofemoral vein (also known as the May-Thurner syndrome).
Venous occlusive disease	Any pathologic process that occurs from underlying stenosis or occlusion of the veins.

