**Note: If core laboratory is unable to assess the venographic evidence, site reported data will be used.**

- 4. Primary Patency at 24- and 36 months:** Freedom from occlusion of the stented segment of the target lesion, freedom from restenosis ≥50% of the stented segment, and freedom from clinically driven target lesion revascularization (CD-TLR).
- 5. Primary Assisted Patency at 12-, 24- and 36 months:** Uninterrupted patency of the stented segment of the target lesion with a secondary intervention, also known as an adjunctive treatment (e.g. balloon venoplasty, subsequent stenting, etc.).
- 6. Secondary Patency at 12-, 24-, and 36 months:** Patency of the stented segment of the target lesion after subsequent intervention for an occlusion.
- 7. Target Lesion Revascularization (TLR) through 30 days, 6-, 12-, 24- and 36 months:** Any re-intervention of the stented segment of the target lesion.
- 8. Major Adverse Events (MAE) through 6-, 12-, 24- and 36 months:**  
MAEs include:
  - All-cause death occurring post-procedure
  - Clinically significant (i.e. symptomatic, confirmed by CT pulmonary angiography) pulmonary embolism
  - Major bleeding complication (post-procedural)
  - Stent thrombosis confirmed by imaging as assessed by core laboratory
  - Stent migration confirmed by imaging as assessed by core laboratory

**Note:** Migration excludes stent dislodgement at the index procedure as may occur with under-sizing of a stent

All MAEs will be adjudicated by a CEC, except stent thrombosis and stent migration which are confirmed by the core laboratory.

---

 Confirmed by Duplex ultrasound scan evaluated by independent core laboratory. In cases where both DUS and venography were used at the same time point, venography would be used for the primary assessment.

[figure not shown]
**9. Delayed Stent Migration at 12-, 24-, and 36 months:** position change of a venous stent observed with an imaging modality > 1 cm from its original location at the conclusion of the index procedure, as determined with regard to a reference anatomic structure.

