**10. Stent Fracture at 30 days, 12-, 24- and 36 months:**

Fracture or breakage of any portion of the stent.

Determined by X-ray for the first 30 subjects at 30 days and for all subjects (including the first 30 subjects) at 12-, 24- and 36 months using the following classifications as adjudicated by a venous stent fracture core laboratory:

- i. Type 0 – No strut fractures
- ii. Type I – Single tine fracture
- iii. Type II – Multiple tine fractures
- iv. Type III – Stent fracture(s) with preserved alignment of the components
- v. Type IV – Stent fracture(s) with mal-alignment of the components
- vi. Type V – Stent fracture(s) in a trans-axial spiral configuration

**11. Change in VEINES-QOL/Sym Score at 6-, 12-, 24- and 36 months:** Defined as the change in VEINES-QOL/Sym score at 6, 12, 24, and 36 months compared to baseline.

**12. Change in VILLALTA Score at 6-, 12-, ,24-, and 36 months:** Defined as the change in VILLALTA score at 6, 12, 24, and 36 months compared to baseline.

**13. Change in EQ5D Quality of life Score at 6-, 12-, 24-, and 36 months:** Defined as the change in Quality of Life Score as assessed by EQ5D questionnaire at 6, 12, 24, and 36 months compared to baseline.

**14. Change in VCSS Score at 6-, 12-, 24-, and 36 months:** Defined as the change in VCSS Score at 6, 12, 24, and 36 months compared to baseline.

**15. Major bleeding complication at 30 days, 6-, 12-, 24- and 36 months:** A blood loss leading to transfusion of whole blood or red cells provided hemoglobin drop of 3 g/dL (1.86 mmol/L) or more is related to bleeding occurring during the index procedure through 36 months post-index procedure.

**16. Medical resource utilization through 36 months** including length of stay and re-hospitalizations.

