**Table X. Periprocedural (≤30 day) safety events**

Clinical Category	Major Hemorrhage	False Aneurysm	Arteriovenous Fistula	Wound Hematoma
Acute	1.8%	0.0%	0.7%	0.4%
Post-thrombotic	0.6%	0.3%	0.1%	1.0%
Non-thrombotic	0.1%	0.1%	0.0%	1.3%
Mixed, Acute & Chronic	3.0% 	0.0%	0.0%	17.2% 
Mixed; PT and NT	0.8%	0.3%	0.0%	1.6%
All Stent Publications	1.1%	0.2%	0.1%	3.6%

 The high rate of Major Hemorrhage in the Mixed, Acute and Chronic group is skewed the Mewissen series (Radiology, 1999) where all patients were treated with thrombolytic agents prior to stenting. Excluding the Mewissen data, the rate of major hemorrhage falls to 0.9% for the Mixed, Acute and Chronic cohort and to 0.7% overall.

 The high frequency of wound hematoma is principally a result of the Mewissen series (Radiology, 1999) where all patients were treated with thrombolytic agents prior to stenting. Excluding the Mewissen article, the frequency of wound hematoma falls to 2.0% for the Mixed, Acute and Chronic cohort and to 1.2% overall.

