### 7.9.3 Secondary Endpoints

To assess how the subjects are doing clinically, the following secondary endpoints will be evaluated. All secondary endpoints will be evaluated using descriptive statistics. No inferential analyses are planned. Detailed analysis methods for core laboratory endpoints and endpoints assessed by office visits can be found in Section 10.

In addition, time-to-event analysis will be performed and Kaplan Meier (KM) estimates with two-sided 95% confidence interval using Peto formula will be reported for major adverse events (MAE) and its component events through 12 months, and annually through 36 months.

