### 10.3.1 Clinical/Safety Endpoints

Clinical/safety endpoints include repeat revascularization procedure on target lesions/vessels and safety endpoints including MAEs (composite and individual components). Most of the event rates of the clinical/safety endpoints will be calculated on patient basis and for different reporting time points, the corresponding cutoff days will be used: 30 days for 30-day; 180 days for 6-month; 360 days for 12-month; 720 days for 24-month; and 1080 days for 36-month.

For each visit (or reporting time point), the event rate will be calculated as the proportion of number of subjects with certain event term over the number of evaluable subjects, the denominator of the event rate calculation will be event specific. The evaluable subjects at each reporting time point include all subjects who are included by the snapshot date and

- 1) Had an event within (on or before) the reporting cutoff days, or
- 2) Had a follow-up at or after the lower limit of the reporting window, or
- 3) The withdrawal consent date/recorded lost-to-follow-up date at or after the lower limit of the reporting window

'Days to event' (date of earliest event – date of index procedure) and 'Days to last contact' (date of last contact – date of index procedure) are usually used for the determination of the eligibility of the 'evaluable subject'. The last contact date will be calculated based on the information gathered from all available dates during the follow-ups.

The 'Reporting Cutoff Days', 'Lower limit of the Reporting Window' and the correspondent visits are as the following:

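### The secondary MAE composite through 6 to 36 months counts major bleeding only from day 30 but its other four components from the index procedure, so first-month bleed-only subjects drop out of the later rates

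*Protocol*

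**What the plan says.** Protocol 6.3.2 (secondary endpoint 8), Protocol Appendix B (secondary-endpoint MAE definition) and SAP 7.9.3 (secondary endpoint 7) list the same five components. In all three places the bleeding component is "Major bleeding complication (post-procedural" type.

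Appendix B defines three bleeding terms that differ only in their time window:
- **Procedural**, used in the 30-day primary composite: "related to bleeding occurring during the index procedure through 30 days post-index procedure".
- **Post-procedural**, used in the secondary composite: bleeding that "is related to bleeding occurring at 30 days through 36 months post-index procedure".
- **Unqualified**, used in the stand-alone bleeding endpoint: index procedure through 36 months.

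The other components carry no day-30 start. Stent thrombosis is "Occlusion of the stented venous segment occurring at any time following stent placement". A single migration definition serves both composites and begins when the index procedure ends. Death counts from after the procedure. Pulmonary embolism has no stated start day, and its wording is the same in both composites.

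On counting, SAP 10.3.1 treats a subject as evaluable with an event if the subject "Had an event within (on or before) the reporting cutoff days", with no lower bound, at days 180, 360, 720 and 1080. SAP 7.9.3 adds Kaplan-Meier estimates that "will be reported for major adverse events (MAE) and its component events through 12 months, and annually through 36 months".

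**The concern.** An MAE rate through a given month should include everyone who has had an MAE by then. Here four components accumulate from the procedure and one from day 30, so the composite is neither cumulative nor a day-30 landmark. Subjects whose only event was a first-month bleed count in the 30-day figure and revert to event-free at 6 months.

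The 30-day rate and the later rates are therefore on different scales, and the cumulative composite is understated. A cumulative rate should not be able to fall over time, but this one can. Long-term safety is a stated purpose of the post-approval phase, and a reader who takes the 12- or 36-month MAE figure alone would not know that early bleeds are missing from it.

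**Working it through.** **1. The plan's own safety figure.** SAP 6.3 gives N = 193, reject if 15 or fewer events, null rate 12.5%, expected rate 5.6%. The exact binomial lower tail P(X ≤ 15) is 0.0249 at 12.5% and 0.9233 at 5.6%, matching the stated alpha and power. That test uses the procedural bleeding term, so the issue here does not affect it. The secondary composite has no stated sample size or power to reproduce.

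**2. Component windows side by side.**

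| Component | 30-day MAE | MAE through 6 to 36 months |
|---|---|---|
| Death | after procedure | after procedure |
| Pulmonary embolism | no start day stated | no start day stated |
| Stent thrombosis | any time after placement | any time after placement |
| Stent migration | after index procedure | after index procedure |
| Major bleeding | index procedure to day 30 | **day 30 to 36 months** |

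Taking a subject with one transfused day-1 bleed and nothing else, the 30-day composite counts an event and the composite at days 180, 360, 720 and 1080 counts none. No rule in either document carries procedural bleeds forward. Both bleeding windows also include day 30, so a day-30 bleed falls in both.

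**3. Expected number dropped.** Inputs are 200 implanted subjects (Protocol Synopsis) and the literature rates in Protocol Appendix A. Table IV's weighted components add to the planning rate: 0.0 + 2.9 + 1.4 + 0.2 + 1.1 = 5.6%. Bleeding is 1.1/5.6 = 20% of it. A Table X footnote says that without one thrombolysis series "the rate of major hemorrhage falls to 0.9% for the Mixed, Acute and Chronic cohort and to 0.7% overall". If each bleed is the subject's only MAE:
- At 1.1%: 200 × 0.011 = 2.2 subjects; P(at least one) = 1 − 0.989^200 = 0.89.
- At 0.7%: 200 × 0.007 = 1.4 subjects; P(at least one) = 1 − 0.993^200 = 0.75.

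**4. Chance that the later rate falls below the 30-day rate.** Let B be the number of bleed-only first-month subjects and E the number with a new event after day 30, treated as mutually exclusive (multinomial, N = 200). The later rate is lower when B > E. The documents give no later-event rate. A rough 12-month proxy is occlusion, 100 − 93.8 = 6.2% from primary-assisted patency, minus 2.9% stent thrombosis at 30 days, or 3.3%. The other later risks are assumptions.

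| Risk of a new event after day 30 | P(B > E), bleeding 0.7% | P(B > E), bleeding 1.1% |
|---|---|---|
| 1% | 0.27 | 0.44 |
| 2% | 0.08 | 0.17 |
| 3% | 0.022 | 0.060 |
| 3.3% | 0.015 | 0.043 |
| 5% | 0.001 | 0.005 |

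**The case against.** The strongest reply is that nothing is lost. First-month bleeds count in the primary composite and again in the stand-alone endpoint, "Major bleeding complication at 30 days, 6-, 12-, 24- and 36 months", which starts at the index procedure. The secondary composite is descriptive, has its own definition and has no 30-day time point, so no planned analysis compares the two. On this view a footnote is enough. This stands as a limit on severity, but it does not repair the composite: a subject-level rate cannot be rebuilt from separate component rates without knowing how many bleeders also had another component.

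A second reply is that the split was deliberate, since each composite uses its own term consistently. Avoiding double counting does not explain it, because first-month deaths, emboli, thromboses and migrations count in both composites.

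Third, the day-30 start appears only in Appendix B. The SAP carries the label without defining it, and the embolism start is inferred from identical wording and the counting rule. That is correct, but the documents offer no other definition of the label.

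Fourth, the size may be overstated. Weighting Table X by the case mix in SAP 6.4 gives 0.26 × 1.8 + 0.30 × 0.1 + 0.44 × 0.6 = 0.76%, about 1.5 of 200, which lies within the range above. Eligibility also excluded bleeding diathesis and required no bleeding after treatment of acute thrombus. The later-risk proxy covers occlusion to 12 months only, so a falling rate becomes less likely as follow-up lengthens.

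Finally, redefining an endpoint after the 12-month data were submitted has an integrity cost. This is fair, and is why both versions should be reported.

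**Conclusion.** The concern holds. Followed exactly, the plan leaves first-month bleed-only subjects out of every MAE rate and curve from 6 to 36 months. This is an inconsistency in the definition and does not depend on any assumed rate.

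Its likely size is small: 0.7 to 1.1 percentage points, or about 1.4 to 2.2 of 200 subjects, at each later time point. This assumes that no bleeder has another MAE component and that literature rates based on BARC type 3a or greater are a fair stand-in for the trial's transfusion-and-hemoglobin definition. An actual fall below the 30-day rate has a probability of about 2% to 6% at a 3% later risk; it becomes substantial (27% to 44%) only if that risk is near 1%. The primary safety test and the study success criteria are unaffected. The change should be made, but nothing confirmatory depends on it.

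**What to change.** In Protocol 6.3.2 secondary endpoint 8, the secondary-endpoint MAE definition in Appendix B, and SAP 7.9.3 secondary endpoint 7, replace the post-procedural bleeding term with the unqualified Appendix B term that runs from the index procedure through 36 months. Keep procedural and post-procedural bleeding as separate component rows, and assign day 30 to one of them.

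Because 6- and 12-month data were collected and submitted under the current definition, report that version alongside, labelled as excluding major bleeding before day 30. Record the change and its reason in the Clinical Study Report, as SAP 7.12 requires.

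The cost is a phrase in three places, one extra table row and a documented change made after the 12-month data were submitted. No new data, adjudication or hypothesis test is needed. The reported 6- to 36-month MAE rates will rise slightly if any such subjects exist.
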